15.2 ADMINISTRATIVE MONITORING

Administrative monitoring procedures will ensure that study OVDs, subjects, and forms can be traced and will allow monitoring of investigator progress and compliance. Accountability and traceability of study OVDs will be monitored by AMO personnel.

Device Accountability

Complete OVD accountability will be maintained at the investigative site by maintaining records of all OVDs received from and returned to AMO. A site log will be used to track OVDs for date of receipt, use and disposition/return to AMO. This site log and any other OVD information will be maintained in the operative room study binder and monitored by AMO personnel. During periodic site monitoring visits, AMO personnel will review

inventory records and logs to ensure OVD accountability compliance and complete OVD traceability.

Site Monitoring Plan

Prior to performing any study surgeries, the requirements of the study and reporting mechanisms will be explained to each investigator either personally at the investigative site or at a formal study investigator meeting. When necessary, a pre-study site qualification visit may be performed to assess the adequacy of the site to perform the study for sites that have not previously worked with AMO or have undergone significant changes, or have not been visited in the past year. A study initiation visit will be conducted for all sites prior to or at the time of the first study surgery.

Throughout the duration of the study, site visits to monitor compliance to this protocol will be made at each site. During a routine site monitoring visit, AMO will review informed consent documents and subject eligibility, and the data on study case report forms will be verified against subject charts and other source documents to ensure complete and accurate reporting. The subject files will also be reviewed to assure that all adverse events and any issues encountered with AMO products have been reported in a timely fashion.

AMO will also review source documents to verify that all required items have been documented in the subject medical charts. Refer to Section 14.1, Source Documents, for a list of items that are required for source documentation. Upon study completion, a final close-out site visit to each site will be made to monitor the last of the subject data records and finalize any outstanding study issues.

A separate Study Monitoring Plan will be established prior to study start that will define the type and frequency of monitoring visits and frequency of record monitoring.

15.3 SAFETY MONITORING

This study will use a Data Safety Monitoring Board (DSMB) for safety monitoring. In alignment with ISO 14155:2011(E), the DSMB is an independent committee that is established by AMO to assess, at intervals, the progress of the clinical investigation, the safety data, or the critical performance endpoints, and to recommend to the sponsor whether to continue, suspend, or stop the clinical investigation. The DSMB will have access to the randomization code to be able to assess safety by OVD group if required. The responsibilities of the DSMB will be detailed in a separate written procedure to establish the frequency of meetings, handling of emergency situations and documentation of such meetings.

This study will also utilize a Medical Monitor for safety monitoring. The Medical Monitor will remain masked until the final study visits have been completed. The Medical

Monitor will review and assess any reports of serious and/or device-related adverse events as well as device deficiencies that could have led to a serious adverse event. If necessary, the medical monitor will discuss these events with the reporting investigator(s), without being specific about OVD type. If unmasking is required by the Medical Monitor to protect the safety of the subject(s), a request will be submitted and approved by Head of Clinical Research and Head of Biostatistics prior to release of the randomization code for only the subject(s) involved, and the IRB will be notified. The medical monitor will also be available to answer all questions from investigators. The medical monitor, as well as any other qualified personnel designated by AMO, shall also review interim progress reports, as applicable.

16. PUBLICATIONS

Refer to the Clinical Trial Agreement for information regarding AMO publication policies.

17. RISK ANALYSIS

POTENTIAL RISKS AND RISK MANAGEMENT

RISKS OF THE BACTERIALLY-DERIVED HEALON5 OVD

The bacterially-derived Healon5 OVD is intended for use in anterior segment ophthalmic surgical procedures of the human eye. Like the non-investigational, animal-derived Healon5 OVD, the bacterially-derived Healon5 OVD is designed to create and maintain a deep anterior chamber which facilitates manipulation inside the eye with reduced trauma to the corneal endothelium and other ocular tissues. The Healon5 OVD can also be used to efficiently separate and control ocular tissues. The Healon5 OVD is not designed to have any pharmacological effect.

Complete removal of the Healon5 OVD (both bacterial-and animal-derived) is important to avoid intraocular pressure peaks (or spikes) postoperatively. Due to the greater concentration of sodium hyaluronate in the Healon5 OVD, the rise in IOP may be higher with the Healon5 OVD (either bacterial-or animal-derived) than if the same volume of other sodium hyaluronate viscoelastic products, with lower zero-shear viscosity, is left in the anterior chamber of the eye. Long-term risks of IOP spikes include secondary glaucoma, visual field loss and optic nerve damage.

GENERAL RISKS OF CATARACT SURGERY AND IOL IMPLANTATION

There are risks and complications associated with cataract surgery and IOL implantation in general. These can include worsening of vision, hemorrhage, loss of corneal clarity, inflammation, infections, retinal detachment, pupil changes, glaucoma, etc. Complications can result in poor vision, loss of vision or loss of the eye.

RISK MANAGEMENT

Subjects will be closely monitored throughout the trial duration. The occurrence of adverse events and complaints will be assessed at each study visit and reported to AMO according to Section 11.0, Adverse Events and Product Complaints. Additionally, AMO will monitor incoming data following the procedures outlined in Section 15.0, Monitoring. Both the DSMB and the Medical Monitor will ensure subjects are not exposed to additional risks by monitoring serious adverse events, device-related adverse events, and device deficiencies that could have led to serious adverse events (Section 15.3, Safety Monitoring).

POTENTIAL BENEFITS

The general clinical performance of the bacterially-derived Healon5 OVD is expected to be the same as the currently-available, animal-derived Healon5; however, without the concerns of cross-over contamination. Bacterially-derived Healon5 is designed to create and maintain a deep anterior chamber, which facilitates manipulation inside the eye with reduced trauma to the corneal endothelium and other ocular tissues. It can also be used to efficiently separate and control ocular tissues.

CONCLUSION

The hazards/risks associated with the bacterially-derived Healon5 are acceptable and within those of the currently-available, animal-derived Healon5. The potential clinical benefits of the bacterially-derived Healon5 outweigh the residual risks when the device is used as intended.

18. RECORDS RETENTION

All study-related correspondence, subject records, consent forms, Authorization for Use/Disclosure of Health Information Forms, records of the distribution and use of all study products, and EDC case report forms should be maintained by the investigator.

The investigator must maintain and have access to the following essential documents until notified by the Sponsor. Note: This may be for a minimum of 15 years after completion of the study. AMO requires notification if the investigator wishes to relinquish ownership of the data so that mutually-agreed-upon arrangements can be made for transfer of ownership to a suitably-qualified, responsible person.

- All case report forms within the EDC system
- All adverse event information (SAE/ADE Detailed pages, follow-up letters, etc.)
- Investigational supply records/inventory
- IRB and regulatory approval documentation
- Study correspondence

- Study agreements
- Site visit documentation
- Protocol(s) and the reason for any deviations from the protocol
- Subject log(s)
- Clinical Investigator's Brochure
- Completed subject informed consent forms and medical privacy forms (e.g., Authorization for Use/Disclosure of Health information)
- Subject medical chart/clinic notes

19. TERMINATION OF THE INVESTIGATION

The clinical investigation will be suspended in the event of high levels of complications and/or adverse events that are unexpected in nature and/or severity and evaluated as to causality relative to the study device. The clinical investigation may be suspended if the DSMB, Medical Monitor or IRB, upon review and evaluation of the clinical data, finds unacceptable clinical performance or the level of single or total complications and/or adverse events unacceptable for continuation of the investigation (such as if any subject has an IOP \geq 30 mmHg at one week postoperatively or later).

If causality is shown not to be related to the study device, the study may be resumed in accordance with the IRB and regulations of the FDA. The study will be terminated if causality is shown to be related to the study device.

Additionally, the investigator, or AMO, may stop a subject's participation at any time. AMO may also stop the study at any time for reasons it determines appropriate. However, no suspension of the study would be made to disadvantage the study subjects. Following suspension of the study for any reason, all study subjects who have already received treatment would continue to be followed through completion of the study visit schedule.

20. STATISTICAL METHODS

This section highlights the analyses for the primary study endpoint and for other key endpoints. The 3-month postoperative visit is the critical analysis time point for all endpoints unless stated otherwise.

20.1 ANALYSIS POPULATION

For the primary endpoints of cumulative IOP rate and mean percent ECC change, the primary analysis population will be an Intent-to-Treat (ITT) population. The ITT population will include all subjects who were randomized and had surgeries using a test OVD in one eye and a control OVD in the other eye. For randomized subjects who received study OVDs but did not have data available at a specific postoperative visit

(i.e., missing postoperative data), data imputation will be performed using MCMC multiple imputation techniques¹. Per-protocol and sensitivity analyses (e.g., worst-case, best-case and tipping-point analysis) will also be provided for the primary IOP and ECC endpoints. Sensitivity analyses will include all randomized subjects whether a study OVD was used or not. The safety population (SP) will include available subjects who had one or both study OVDs with available data at the time of analysis (i.e., no data imputation). Only the safety population will be used for analyses of secondary safety endpoints and other endpoints. For the secondary safety endpoints, no multiplicity or imputation will be done since they are considered safety endpoints and are not intended for claims. Only safety population (SP) will be used for the secondary safety endpoints.

20.2 STUDY ENDPOINTS

Primary Endpoints

SAFETY: CUMULATIVE RATE OF IOP SPIKES 30 MMHG OR GREATER MEASURED POSTOPERATIVELY

The cumulative frequency and proportion of eyes with an IOP spike will be reported for both OVD groups for safety population, PP population and sensitivity analysis. For ITT (with data imputation), only the difference between the OVD groups will be reported. The difference in the cumulative IOP spike rate will be analyzed by the McNemar test using a GLIMMIX procedure taking into account the paired data. The GLIMMIX model will model spike as the dependent variable and OVD group as an independent variable and include the SUBJECT = option for the paired eye data. The hypothesis testing of non-inferiority for cumulative percentage of IOP spikes will be tested using a 1-sided, McNemar test at an alpha of 0.025 with a delta of 0.10 (10%). The null hypothesis is that the paired difference between eyes is less than or equal to -10%. The alternative hypothesis is that the paired difference between eyes is greater than -10%.

$$H_0: p_c - p_t \leq \delta$$

$$H_a: p_c - p_t > \delta$$

where...

p_t = Test rate of IOP spikes 30 mm Hg or greater

p_c = Control rate of IOP spikes 30 mm Hg or greater

δ = non-inferiority margin: -10%

Success Criteria: If the lower 2-sided 95% confidence interval (equivalent to the 1-sided 97.5% CI) for the difference between the proportions is greater than -10%².

EFFECTIVENESS: MEAN PERCENT ECC CHANGE PREOPERATIVELY VS. POSTOPERATIVELY

The mean percent change in ECC from preoperative to 3 months postoperative will be reported by descriptive statistics for both OVD groups for safety population, PP

population and sensitivity analysis. For ITT (with data imputation), only the mean difference between the two OVD groups will be reported. The percent change in ECC from preoperative to postoperative is calculated as followed:

$$\text{Percent change in ECC} = (\text{Postop ECC minus Preop ECC})/\text{Preop ECC}$$

The difference in mean percent change in ECC will be analyzed by a paired t-test. The hypothesis testing of non-inferiority for mean percent ECC change will be tested using a 1-sided, paired t-test at an alpha of 0.025 and a delta of 5%. The null hypothesis is that the paired mean difference for mean percent change in ECC is equal to or less than -5%. The alternative hypothesis is that the paired mean difference in percent change between eyes is greater than -5%.

$$H_0: \mu_{\text{test}} - \mu_{\text{control}} \leq \delta$$

$$H_a: \mu_{\text{test}} - \mu_{\text{control}} > \delta$$

where...

μ_{test} = ECC percent change in test OVD

μ_{control} = ECC percent change in control OVD

δ = non-inferiority margin: -5%

Success Criteria: If the lower 2-sided 95% confidence interval (equivalent to 1-sided 97.5% CI) for the mean difference between eyes in percent change for ECC is greater than -5%.

If the distribution of the percent ECC change does not meet the normality assumption, a non-parametric test will be performed to evaluate the non-inferiority of ECC endpoint. A similar alpha level of 0.025 and a delta of 5% will be used for the 1-sided non-parametric test.

In addition, ECC for preoperative, 3 months postoperative and the difference between preoperative and 3 months will also be reported as supportive data using the safety population.

Secondary Safety Endpoints

Serious and/or device-related adverse events will be tabulated with the frequency and proportion of eyes with these events reported over time for both OVD groups. The adverse event rates will be compared to the ISO SPE rates. Comparison of the ISO SPE rates will be performed using an exact test based on the binomial distribution. The null hypothesis is that the study rate for test OVD is equal or lower than the ISO SPE rate, and the alternative hypothesis is that the study rate for test OVD is greater than the ISO SPE rate.

The grades of inflammation (for epithelial and stromal edema, cells and flare, anterior and posterior synechiae, and fibrin presence) will be tabulated with the frequency and proportion of eyes with each grading for each event over time and cumulatively will be presented for both OVD groups.

For the percentage of IOP spikes at 6 hours, 1 day, 1 week, 1 month and 3 months postoperatively, a 1-sided, McNemar test of non-inferiority of proportions will be performed at an alpha of 0.025 with a delta of 0.10 (10%). This analysis is similar to the approach used for the primary endpoint of cumulative percentage of IOP spikes.

The change in IOP from baseline will be presented by descriptive statistics for the 6-hour, 1-day, 1-week, 1-month and 3-month postoperative time points by OVD group.

Other endpoints, optical/visual symptoms (non-directed) and medical findings/adverse events (non-serious, non-device-related) will be tabulated with frequency and proportion over time and cumulatively by OVD group.

The frequency and proportion of monocular BCDVA will be reported over time by visual acuity line. Monocular BCDVA percent 20/40 or better will also be compared to ISO SPE rate.

The frequency and proportion of monocular UCDVA at 1 day will be reported by visual acuity line.

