20.3 GENERAL STATISTICS

Descriptive statistics will typically include sample size (N), mean, standard deviation (SD), minimum (Min) and maximum (Max) as appropriate for continuous variables. For dichotomous variables, the frequency and proportion will be reported and McNemar's test will be applied. For continuous variables, statistical tests (paired t-test) assuming normality will generally be used. For ordinal categorical data, the frequency and proportion will be reported and Wilcoxon signed-rank test will generally be applied.

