2.3 DATA CONVENTIONS

Descriptive statistics will typically include sample size (N), mean, standard deviation (SD), median, minimum (Min.), and maximum (Max.) as appropriate for continuous variables. For categorical data, the frequency and proportion will be computed.

For continuous variables, statistical tests assuming normality will generally be used. However the data will be reviewed to evaluate whether the normality assumption is appropriate. If it is found not to be appropriate, either an appropriate transformation of the data (i.e., logarithmic) may be used or the corresponding non-parametric tests may be used. Deviations from the proposed statistical guidelines will be substantiated by sound statistical rationale. In this study, unless otherwise indicated, paired t-tests will be used for continuous data, Wilcoxon signed-rank test for ordinal data and McNemar's test for dichotomous data.

Unless otherwise indicated, alpha will be set to 0.05 for two-sided statistical testing with alpha set to 0.025 for one-sided testing.

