2.5 MULTIPLICITY ADJUSTMENT

No multiplicity adjustment is planned for the primary endpoints since both endpoints are required to meet statistical significance. No multiplicity adjustment is planned for the secondary safety endpoints as these are safety endpoints not intended for claims. Please see Section 6 for more details regarding the planned analysis of secondary safety endpoints.

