6.2 DISTRIBUTION AND GRADE OF INFLAMMATION

The grades of inflammation (for epithelial and stromal edema, cells and flare, anterior and posterior synechiae, and fibrin presence) will be tabulated with frequency and proportion of eyes with each grading for each event presented over time and cumulatively for both OVD groups.

6.3 RATE OF IOP SPIKES 30 MMHG OR GREATER AT 6 HOURS, 1 DAY, 1 WEEK, 1 MONTH AND 3 MONTHS POSTOPERATIVELY

The rate of IOP spike 30 mmHg or greater at 6 hour, 1 day, 1 week, 1 month and 3 months postoperatively will be tabulated with frequency and proportion by OVD group and analyzed using the McNemar test.

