| Mean difference between OVD groups in percent ECC change preoperatively vs. 3 months (N, Mean, SD, Median, Min., Max, 95% CI.) | X | X | ITT/Sensitivity/SF/PP |
| Mean percent change of ECC preoperatively vs. 3 months (N, Mean, SD, Median, Min., Max, 95% CI.) by OVD groups | | | Sensitivity/SF/PP |
| SECONDARY SAFETY ENDPOINTS | | | |
| Serious and/or device related adverse event rates (No. and percent) compared to ISO SPE rates | X | X | SF |
| Serious and/or device related adverse event rates over time (No. and percent) | | | |
| Grades of inflammation (No. and percent) over time and cumulatively (epithelial and stromal edema, cells and flare, anterior and posterior synechiae, fibrin presence) | X | X | SF |
| IOP 30mmHG spike rate (No. and percent, 95% CI) between OVD groups at 6 hour, 1 day, 1 week, 1 month and 3 months postoperatively | X | X | SF |
| Change of IOP from baseline at 6-hour, 1-day, 1-week, 1-month, and 3-month postoperatively between OVD groups (N, Mean, SD, Median, Min, Max.) | X | X | SF |
| ADDITIONAL ENDPOINTS | | | |
| Non-directed ocular visual symptoms (No. and percent) over time and cumulatively | X | X | SF |
| Other AE (non-serious, non-device related)/Medical findings (No. and percent) over time and cumulatively | X | X | SF |
| Monocular BCDVA by acuity line over time (No. and percent) | X | X | SF |
| Percent 20/40 or better vs. ISO SPE rate | | | |
| Monocular UCDVA by acuity line at 1 day (No. and percent) | X | X | SF |
| Other IOP/ECC Tables | | | |
| IOP at preoperative, 6 hour, 1 day, 1 week, 1 month and 3 month (N, Mean, SD, Median, Min., Max) | X | X | SF |
| ECC at preoperative, 3 months and difference between preoperatively vs. 3 months (N, Mean, SD, Median, Min., Max) | X | X | SF |
| Other Adverse Event Tables | | | |
| Non-adverse event/procedures (No. and Percent) | X | X | SF |
| Listing of serious and/or device-related Adverse Events by event and by OVD type (include site, age, last reported BCDVA, complications) | X | X | SF |
| | | | |

KEY:OVD=viscoelastic used, VA=Visual acuity, UCDVA=Uncorrected distance visual acuity, BCDVA=Best corrected distance visual acuity, ITT=Intent to Treat, PP=Per protocol, SF=Safety, SD=Standard deviation, Min.=Minimum value, Max.=Maximum value, C.I.=Confidence interval, X=Tables will be provided – blank indicates table will not be generated for that group, 3M=3-month postoperative visit

TIME FRAME: The 3-month postoperative visit is the key timeframe for reporting.

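### Does reusing the 10-point non-inferiority margin for IOP spikes at each of five visits, when SAP 6.3 names only the McNemar test, call for a change?

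*Protocol*

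**What the plan says.** Protocol 20.2, under the secondary safety endpoints, covers spikes at five separate visits and says that "a 1-sided, McNemar test of non-inferiority of proportions will be performed at an alpha of 0.025 with a delta of 0.10 (10" percent). It then adds: "This analysis is similar to the approach used for the primary endpoint of cumulative percentage of IOP spikes". The hypotheses for that primary analysis appear earlier in the same section: "The null hypothesis is that the paired difference between eyes is less than or equal to -10" percent, with the difference taken as control minus test.

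SAP 6.3 is shorter. It says that the per-visit rates "will be tabulated with frequency and proportion by OVD group and analyzed using the McNemar test". SAP 2.5 tells the reader "Please see Section 6 for more details regarding the planned analysis of secondary safety endpoints", but Section 6 gives no margin, sidedness or alpha for this endpoint. The general conventions are equally brief: SAP 2.3 lists "McNemar's test for dichotomous data" as the default unless otherwise indicated, and Protocol 20.3 says "the frequency and proportion will be reported and McNemar's test will be applied". SAP Appendix I lists the output as "IOP 30mmHG spike rate (No. and percent, 95% CI) between OVD groups at 6 hour" and the four later visits.

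The only spike rate in either document is the 30% in Protocol 20.5 and SAP 8. It belongs to the cumulative, any-visit endpoint.

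**The concern.** Two things look wrong on a first reading.

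- **Margin.** Ten points is one third of a 30% rate. If spikes at 1 week or later occur in only about 1% of eyes, ten points is ten times the rate, and a clear excess in test eyes could be labelled non-inferior. This sits awkwardly beside Protocol 19, which gives a single subject with a spike at one week or later as an example of a finding that may suspend the study.
- **Wording.** Someone working from SAP 6.3 alone, with the SAP 2.3 default, could run an ordinary McNemar test of no difference. That is a different hypothesis from the one in Protocol 20.2.

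At stake would be the stated conclusion at each visit, and which of two tests produces it.

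**Working it through.** **Inputs.** Margin 10 points and one-sided alpha 0.025 (Protocol 20.2). Cumulative rate 30%, correlation 0.5, power 0.80 and n = 195 (Protocol 20.5, SAP 8). About 200 evaluable pairs (SAP 1). Per-visit rates are not given; the 1% to 5% used below is an assumption. The documents do not name an interval method for the paired difference, so score (Tango) and Wald are both shown.

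**The plan's own figure.** For 30% v 40% with correlation 0.5, the both-spike cell is 0.30 × 0.40 + 0.5 × √(0.21 × 0.24) = 0.232. The discordant cells are then 0.40 − 0.232 = 0.168 and 0.30 − 0.232 = 0.068. An exact one-sided McNemar test at 0.025 with n = 195 has power 0.801, so the stated 195 reproduces. The shifted-null non-inferiority formula with both rates at 30% has both-spike cell 0.09 + 0.5 × 0.21 = 0.195 and discordance 2 × (0.30 − 0.195) = 0.21. It gives n = (1.960 + 0.842)² × 0.21 / 0.10² ≈ 165, so 195 is not short for the cumulative endpoint.

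**The margin at a sparse visit.** Take n = 200, no control-only spikes and c test-only spikes.

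- Score: the restricted estimate of the control-only cell is zero, so z = (c − 200 × 0.10) / √(200 × 0.10 × 0.90) = (c − 20) / 4.243. For c = 11, z = −2.12, which passes (lower limit −0.0958). For c = 12, z = −1.89, which fails (lower limit −0.1019).
- Wald: lower limit = −c/200 − 1.96 × √(c − c²/200) / 200. For c = 13 this is −0.0650 − 0.0342 = −0.0992, which passes. For c = 14 it is −0.0700 − 0.0354 = −0.1054, which fails.

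So 0 v 11 (5.5% of pairs, score) or 0 v 13 (6.5%, Wald) would meet the margin. With independent eyes and assumed true rates of 1% control and 3% test, non-inferiority is declared with probability 0.99 (score) or above 0.99 (Wald). At 1% and 5% the probabilities are 0.84 and 0.91.

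**Where this applies.** At the planned 30% rate and correlation 0.5, 200 × 0.21 = 42 pairs are discordant. That is far from the sparse case above, so the calculation speaks only to low-rate visits.

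**Is any of this an error?** Every true excess used above (2 or 4 points) lies inside a 10-point margin. Passing there is what the rule is designed to do and is not a false-positive rate. The question is only whether 10 points is a useful limit at such a visit.

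**The two texts side by side.** SAP 5.1 uses the same label, the McNemar test, for its own non-inferiority analysis and then gives margin and alpha. SAP 6.3 uses the label without the details. Appendix I asks for a between-group 95% interval at each visit, the form from which the primary criterion is read. The SAP 2.3 default yields where something else is indicated, and Protocol 20.2 indicates it. The texts are unequal in detail and do not contradict each other.

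**The case for a change.** The strongest case for a change is that the Protocol prescribes a non-inferiority test at each visit, so a conclusion will be produced at each visit, and the reason given for the margin is only similarity to the primary analysis. A result of 6 v 0 has an exact two-sided McNemar p of 2 × 0.5⁶ = 0.031, yet it meets the margin easily (score lower limit −0.064). A reader might find it odd to see non-inferior printed beside that split, given how seriously Protocol 19 treats one late spike. Repairing the wording would be cheap.

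Part of this stands. SAP 6.3 does omit the specification that SAP 2.5 promises, and the margin has no per-visit rationale. The rest does not go far. A real difference that lies inside a margin is a coherent pair of findings, and the Protocol specifies no test of no difference for this endpoint beyond the generic default. The rarity of late spikes is assumed. Dropping a pre-specified test at some visits on assumed rates would be a preference about margins on which competent statisticians differ.

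**Conclusion.** No change is called for. The SAP omission is a gap that analysts would fill from Protocol 20.2, which states the test, sidedness, alpha and margin. The single margin is a fair, if debatable, simplification.

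The practical effect is confined to a per-visit label. Protocol 20.1 and SAP 2.5 say these endpoints are not intended for claims. SAP 6.3 has no success criterion, unlike SAP 5.1, 5.2 and 6.1. Late spikes are caught by other routes: each one goes on an SAE/ADE page (Protocol 10.5 and 10.7), is a listed serious anticipated event (Protocol 11.1) tabulated by OVD group (SAP 6.1), and can be examined by OVD group by the DSMB (Protocol 15.3). A spike at any visit also makes its eye a case in the cumulative primary endpoint. The counts and interval in Appendix I would show a 6 v 0 or 11 v 0 split whatever label accompanied it.

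The size, 11 (score) or 13 (Wald) test-only spikes tolerated against none, rests on 200 complete pairs and no control-only spikes. How often such a split would arise depends on late-visit rates that the documents do not give. The primary analyses and the sample size are untouched.
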